## Coagulation Assessments

The following coagulation assessments will be performed:

- Prothrombin time (PT) in international normalized ratio (INR)
- Activated partial thromboplastin time (aPTT)
- Thrombin time (TT)

## Urinalysis

The urinary tests listed below will be performed:

|                  |   |
|------------------|---|
| Bilirubin        | Microscopic exam (To be performed at the discretion of the PI or qualified designee): |
| Blood            | White blood cells   |
| Glucose          | Red blood cells   |
| Ketones          | Epithelial cells  |
| pH               | Casts   |
| Protein          | Bacteria  |
| Specific gravity | Crystals  |
| Urobilinogen     |   |

## Hepatitis B, Hepatitis C and HIV status

Hepatitis B surface antigen, HBcAb, HepCAb, and HIV status will be assessed. If the results show a positive HepCAb, hepatitis C virus RNA by PCR is necessary. The test must be confirmed negative at screening for the subject to be eligible for this study.

## Pregnancy Test (Females Only)

A urinary pregnancy test will be performed on all female subjects at screening; day -1 for cohorts 1 to 5 or day -3 to day -1 for cohorts 6 to 9; for cohort 1 to 7 the end of treatment visit; and for cohorts 8 and 9 at Day 225 and the end of study, as specified in the SOA ([Table 4](#) to [Table 9](#)). Pregnancy tests must be confirmed negative for the subject to be eligible for this study.

## Serum Follicle Stimulating Hormone Test (Females Only)

Additional serum may be collected for an FSH test if required to ensure menopause in a female subject. Results must be consistent with postmenopausal status per local laboratory ranges for inclusion in this study. Postmenopausal status will be recorded on the medical history eCRF.

## Drug Screen

A urine screen for drugs with a high potential of abuse (according to the local lab standards) will be performed at screening; day -1 for cohorts 1 to 5 or day -3 to

day -1 for cohorts 6 to 9; and at the end of treatment visit for cohorts 1 to 7; and for cohorts 8 and 9, on day 365. The following drugs will be tested:

- Tetrahydrocannabinol
- Benzodiazepines
- Cocaine
- Opiates
- Amphetamines
- Barbiturates

Subjects with a positive result at time points specified in the SOA will be excluded from the study at screening. The intention is to detect drugs of abuse and not those prescribed therapeutically. Subjects with a positive drug test may be retested once at the discretion of the Principal Investigator in consultation with the Amgen Medical Monitor. The result will be documented in the source document but will not be recorded on the CRF.

### **Lipid Panel**

A fasting (at least 10 hours) blood sample triglycerides will be assessed at screening and analyzed at the local laboratory.

Fasting (at least 10 hours) blood samples will be collected at all time points indicated as the on-study lipid panel in the SOA ([Table 4](#) to [Table 9](#)). The following analytes will be assessed:

- Total cholesterol
- LDL-C (by ultracentrifugation)
- HDL-C
- VLDL-C
- Triglycerides
- Apolipoprotein A1 (apoA1)
- Apolipoprotein B (apoB)

The following analytes will be collected per the Schedule of Assessments:

#### 10.4 Pharmacokinetic and Pharmacodynamic Analysis

Blood samples for determination of AMG 890 serum concentrations and for the evaluation of plasma Lp(a) dynamic response will be assessed at time points indicated in the Schedule of Assessments ([Table 4](#) to [Table 9](#)). Collection time points may be added or removed based on affluence of data informing the PK of AMG 890 and its PD effects.

For cohorts 1 to 5, urine PK samples for a qualitative assessment of AMG 890 levels will be assessed at the time points indicated in the Schedule of Assessments.

[figure not shown]
- After dosing, all urine passed (including urine passed during bowel movements) must be collected including the first voiding of the following day. Urine will be collected and pooled in 12-hour interval samples from the time of dosing through day 4 (72 hours post-dose) for cohorts 3 to 5, and through day 2 as a 24-hour interval sample after dosing for cohorts 1 and 2. The total volume of urine collected (mL) for each collection interval is to be reported.
- The start and stop time of each collection interval (to the minute) is to be reported.
- The entire interval specimen should be collected in a properly labeled urine container and refrigerated at 2°C to 8°C during collection.
- The subject should be informed that a normal intake of fluids during the collection period is desirable.

The PK and PD samples must be collected within the following windows:

- $\pm$  5 minutes on the first hour assessments on day 1;  $\pm$  10 minutes for the subsequent assessments on the same day (dosing day)
- $\pm$  1 hour on days 2 to 4
- $\pm$  1 day on days 7 through 29
- $\pm$  3 days from day 43 through the end of treatment visit for study visits of cohorts 1 to 7 and through the end study visit for cohorts 8 and 9

[figure not shown]
The precise time of all sample collection should be documented.

Detailed sample collection, processing, storage and shipping instructions are provided in the laboratory manual.

[figure not shown]

#### **10.6 Biomarker Development**

Biomarkers are objectively measured and evaluated indicators of normal biologic processes, pathogenic processes, or pharmacologic responses to a therapeutic intervention. Biomarker development can be useful in developing markers to identify disease subtypes, guide therapy, and/or predict disease severity.

#### **10.7 Pharmacogenetic Studies**

## 10.8 Sample Storage and Destruction

Laboratory samples collected can be analyzed for any of the tests outlined in the protocol and for any tests necessary to minimize risks to study subjects. This includes testing to ensure analytical methods produce reliable and valid data throughout the course of the study. This can also include, but is not limited to, investigation of unexpected results, incurred sample reanalysis, and analyses for method transfer and comparability.

All samples and associated results will be coded prior to being shipped from the site for analysis or storage. Samples will be tracked using a unique identifier that is assigned to the samples for the study. Results are stored in a secure database to ensure confidentiality.

If informed consent is provided by the subject, Amgen can do additional testing on remaining samples (ie, residual and back-up) to investigate and better understand hyperlipoproteinemia(a), the dose response and/or prediction of response to AMG 890, characterize antibody response, and characterize aspects of the molecule (eg, mechanism of action/target, metabolites) and additional insights into cardiovascular disease. Results from this analysis are to be documented and maintained, but are not necessarily reported as part of this study. Samples can be retained for up to 20 years.

Since the evaluations are not expected to benefit the subject directly or to alter the treatment course, the results of pharmacogenetic, biomarkers, biomarker development, or other exploratory studies are not placed in the subject's medical record and are not to be made available to the subject, members of the family, the personal physician, or other third parties, except as specified in the informed consent.

The subject retains the right to request that the sample material be destroyed by contacting the investigator. Following the request from the subject, the investigator is to provide the sponsor with the required study and subject number so that any remaining blood, biomarker, PK, and pharmacogenetic samples can be located and destroyed. Samples will be destroyed once all protocol-defined procedures are completed.

However, information collected from samples prior to the request for destruction, will be retained by Amgen.

The sponsor is the exclusive owner of any data, discoveries, or derivative materials from the sample materials and is responsible for the destruction of the sample(s) at the request of the subject through the investigator, at the end of the storage period, or as appropriate (eg, the scientific rationale for experimentation with a certain sample type no longer justifies keeping the sample). If a commercial product is developed from this research project, the sponsor owns the commercial product. The subject has no commercial rights to such product and has no commercial rights to the data, information, discoveries, or derivative materials gained or produced from the sample.

See Section [14.3](#) for subject confidentiality.

## **11. WITHDRAWAL FROM TREATMENT, PROCEDURES, AND STUDY**

### **11.1 Subjects' Decision to Withdraw**

Subjects have the right to withdraw from the study at any time and for any reason without prejudice to their future medical care by the physician or at the institution.

Subjects (or a legally acceptable representative) can decline to continue receiving investigational product and/or other protocol-required therapies or procedures at any time during the study but continue participation in the study. If this occurs, the investigator is to discuss with the subject the appropriate processes for discontinuation from investigational product, device or other protocol-required therapies and must discuss with the subject the options for continuation of the SOA ([Table 4](#) to [Table 9](#)) including different options of follow-up (eg, in person, by phone/mail, through family/friends, in correspondence/communication with other treating physicians, from the review of medical records) and collection of data, including endpoints, and adverse events. Subjects who have discontinued investigational product and/or protocol required therapies or procedures should not be automatically removed from the study. Whenever safe and feasible it is imperative that subjects remain on study to ensure safety surveillance and/or collection of outcome data. The investigator must document the level of follow-up that is agreed to by the subject.

Withdrawal of consent for a study means that the subject does not wish to receive further protocol-required therapies or procedures, and the subject does not wish to or is unable to continue further study participation. Subject data up to withdrawal of consent will be included in the analysis of the study, and where permitted, publicly available data

can be included after withdrawal of consent. The investigator is to discuss with the subject appropriate procedures for withdrawal from the study.

### **11.2        Investigator or Sponsor Decision to Withdraw or Terminate Subjects' Participation Prior to Study Completion**

The investigator and/or sponsor can decide to withdraw a subject(s) from investigational product, protocol procedures, or the study as a whole at any time prior to study completion.

Subjects may be eligible for continued treatment with Amgen investigational product(s) and/or other protocol required therapies by a separate protocol or as provided for by the local country's regulatory mechanism, based on parameters consistent with Section 15.1.

### **11.3        Reasons for Removal From Treatment, or Study**

#### **11.3.1        Reasons for Removal From Treatment**

Reasons for removal from protocol-required investigational product(s) or procedural assessments include any of the following:

- subject request
- safety concern (eg, due to an adverse event, ineligibility determined, protocol deviation, non-compliance, or pregnancy)
- death
- lost to follow-up
- decision by sponsor (other than subject request, safety concern, lost to follow-up)

#### **11.3.2        Reasons for Removal From Study**

Reasons for removal of a subject from the study are:

- decision by sponsor
- withdrawal of consent from study
- death
- lost to follow-up

## **12.        SAFETY DATA COLLECTION, RECORDING, AND REPORTING**

### **12.1        Definition of Safety Events**

#### **12.1.1        Adverse Events**

An adverse event is defined as any untoward medical occurrence in a clinical trial subject. The event does not necessarily have a causal relationship with study treatment. The investigator is responsible for ensuring that any adverse events observed by the investigator or reported by the subject are recorded in the subject's medical record.

The definition of adverse events includes worsening of a pre-existing medical condition. Worsening indicates that the pre-existing medical condition or underlying disease (eg, diabetes, migraine headaches, gout) has increased in severity, frequency, and/or duration more than would be expected and/or has an association with a significantly worse outcome than expected. A pre-existing condition that has not worsened more than anticipated (ie, more than usual fluctuation of disease) during the study, or involves an intervention such as elective cosmetic surgery or a medical procedure while on study, is not considered an adverse event. Abnormal laboratory findings without clinical significance are usually not considered adverse events. However, laboratory value changes that require treatment or adjustment in current therapy may be considered adverse events.

The investigator's clinical judgment is used to determine whether a subject is to be removed from treatment due to an adverse event. In the event a subject, or subject's legally acceptable representative requests to withdraw from protocol-required therapies or the study due to an adverse event, refer to Section [11.1](#) for additional instructions on the procedures recommended for safe withdrawal from protocol-required therapies or the study.

### **12.1.2        Serious Adverse Events**

A serious adverse event is defined as an adverse event that meets at least 1 of the following serious criteria:

- fatal
- life threatening (places the subject at immediate risk of death)
- requires in patient hospitalization or prolongation of existing hospitalization
- results in persistent or significant disability/incapacity
- congenital anomaly/birth defect
- other medically important serious event

An adverse event would meet the criterion of "requires hospitalization," if the event necessitated an admission to a health care facility (eg, overnight stay).

If an investigator considers an event to be clinically important, but it does not meet any of the serious criteria, the event could be classified as a serious adverse event under the criterion of "other medically important serious event." Examples of such events could include allergic bronchospasm, convulsions, blood dyscrasias, drug induced liver injury (DILI) (see [Appendix A](#) for DILI reporting criteria), or events that necessitate an emergency room visit, outpatient surgery, or urgent intervention.

## 12.2 Safety Event Reporting Procedures

### 12.2.1 Adverse Events

#### 12.2.1.1 Reporting Procedures for Adverse Events That do not Meet Serious Criteria

The investigator is responsible for ensuring that all adverse events observed by the investigator or reported by the subject that occur after the first dose of investigational product through the end of treatment visit are reported using the Event eCRF.

The investigator must assign the following adverse event attributes:

- Adverse event diagnosis or syndrome(s), if known (if not known, signs or symptoms),
- **Did the event start prior to the first dose of investigational product,**
- **Assessment of seriousness,**
- Dates of onset and resolution (if resolved),
- Severity,
- Assessment of relatedness to investigational product, protocol required therapies, and/or study mandated procedures
- Action taken, **and**
- **Outcome of event.**

The adverse event grading scale used will be the Amgen Standard Adverse Event Grading Scale: mild (aware of sign or symptom, but easily tolerated), moderate (discomfort enough to cause interference with usual activity), and severe (incapacitating with inability to work or do usual activity). The grading scale used in this study is described in the [Appendix A](#).

The investigator must assess whether the adverse event is possibly related to the investigational product (AMG 890 or placebo). Relatedness means that there are facts or reasons to support a relationship between investigational product and the event.

The investigator must assess whether the adverse event is possibly related to any study mandated activity (eg, administration of investigational product, protocol-required therapies, use of medical device(s) and/or procedure (including any screening procedure(s)).

The investigator is responsible for reviewing laboratory test results and determining whether an abnormal value in an individual study subject represents a clinically significant change from the subject's baseline values. In general, abnormal laboratory findings without clinical significance (based on the Investigator's judgment) are not to be recorded as adverse events. However, laboratory value changes that require treatment

or adjustment in current therapy are considered adverse events. Where applicable and preferentially, clinical sequelae (not the laboratory abnormality) are to be recorded as the adverse event.

The investigator is expected to follow reported adverse events until stabilization or reversibility.

#### **12.2.1.2 Reporting Procedures for Serious Adverse Events**

The investigator is responsible for ensuring that all serious adverse events observed by the investigator or reported by the subject that occur after signing of the informed consent through the end of study visit (last visit where data for primary endpoints are collected) are recorded in the subject's medical record and are submitted to Amgen. All serious adverse events must be submitted to Amgen within 24 hours following the investigator's knowledge of the event via the Event eCRF and using the paper based Serious Adverse Event Report (SAER) Form (see [Table 10](#) and [Appendix B](#)).

The investigator must assess whether the serious adverse event is possibly related to the investigational product (AMG 890 or placebo). Relatedness means that there are facts or reasons to support a relationship between investigational product and the event.

The investigator must assess whether the serious adverse event is possibly related to any study mandated activity (eg, administration of investigational product, protocol-required therapies, use of medical device(s) and/or procedure (including any screening procedure(s)).

The investigator is expected to follow reported serious adverse events until stabilization or reversibility.

New information relating to a previously reported serious adverse event must be submitted to Amgen. All new information for serious adverse events must be sent to Amgen within 24 hours following knowledge of the new information. If specifically requested, the investigator may need to provide additional follow-up information, such as discharge summaries, medical records, or extracts from the medical records.

Information provided about the serious adverse event must be consistent with that recorded on the Event eCRF.

If a subject is permanently withdrawn from protocol-required therapies because of a serious adverse event, this information must be submitted to Amgen.

To comply with worldwide reporting regulations for serious adverse events, the treatment assignment of subjects who develop serious, unexpected, and related adverse events may be unblinded by Amgen before submission to regulatory authorities.

Amgen will report serious adverse events and/or suspected unexpected serious adverse reactions as required to regulatory authorities, investigators/institutions, and IRBs/IECs in compliance with all reporting requirements according to local regulations and good clinical practice.

The investigator is to notify the appropriate IRB/IEC of serious adverse events occurring at the site and other adverse event reports received from Amgen, in accordance with local regulatory requirements and procedures.

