**Treatment**

After completion of all pre-dose procedures on day 1, subjects will receive their dose of AMG 890 or placebo.

For cohorts 1 to 5, subjects will stay in the research facility for a residency period from day -1 through day 4. For cohort 9, sentinel pair subjects will stay in the research facility for a residency period from day -1 through day 2. After completion of day 4 procedures for cohorts 1 to 5 or completion of day 2 procedures for the cohort 9 sentinel pair, subjects will be discharged and will return to the research facility at specified time points as per the schedule of assessments for additional collection of blood and urine samples for laboratory assessments, PK and PD measurements, and completion of safety assessments through the end of the study.

For cohorts 6 to 8 and cohort 9 (other than the sentinel pair), subjects will not have a required residency period, but will report to the research facility on day 1 for completion of the day 1 scheduled procedures according to the Schedule of Assessments ([Table 4](#) to [Table 9](#)).

All adverse events (including serious adverse events) and use of concomitant medication will be collected throughout the study.

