### 3. Study Glossary

| Abbreviation or Term                | Definition/Explanation   |
|-------------------------------------|--|
| ADA                                 | anti-drug antibody   |
| ALP                                 | alkaline phosphatase   |
| ALT                                 | alanine aminotransferase   |
| Apo(a)                              | Apolipoprotein(a)  |
| ApoA1                               | apolipoprotein A1  |
| ApoB                                | apolipoprotein B   |
| AST                                 | aspartate aminotransferase   |
| AUC                                 | area under the concentration-time curve  |
| AUC last                 | area under the concentration-time curve from time zero to the last quantifiable concentration  |
| BMI                          | body mass index   |
| BP                                  | blood pressure   |
| C max                    | maximum serum concentration  |
| CRF                                 | case report form   |
| DILI                                | drug-induced liver injury  |
| DLRM                                | Dose Level Review Meeting  |
| DLRT                                | Dose Level Review Team   |
| ECG                                 | Electrocardiogram  |
| eCRF                                | electronic case report form  |
| EDC                                 | electronic data capture  |
| eGFR                                | estimated glomerular filtration rate   |
| Enrolled                            | Defined as when the subject has fulfilled all conditions to be randomized and to receive study drug.   |
| End of Study for Individual Subject | Defined as the last day that protocol-specified procedures are conducted for an individual subject.  |
| EOS                                 | end of study - Defined as when the last subject is assessed or receives an intervention for evaluation in the study; if the study includes multiple parts (eg, safety follow-up or survival assessment), the end of study would include these additional parts |
| EOT                                 | end of treatment - defined as the last assessment for the protocol specified treatment phase of the study for an individual subject  |
| FDA                                 | Food and Drug Administration   |
| FIH                                 | first-in-human   |

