## 6.5 Estimated Study Duration

### 6.5.1 Study Duration for Subjects

Subject participation will vary according to enrollment scheme. The duration of the follow-up period for each cohort was defined based on the simulation results from the population K-PD model describing the Lp(a) response to AMG 890 administration developed based on 57-day GLP repeat-dose cynomolgus monkey toxicology and PK/PD studies (Section 5.2.1). Data suggest that the lengths of study participation proposed will allow plasma Lp(a) levels to return at least to 80% of the baseline levels for each subject after administration across the proposed AMG 890 clinical doses.

For cohorts 1 and 2, planned subject participation will last up to 141 days, including a 28-day screening period prior to investigational product (IP) administration and on-study period (through the end of treatment visit) lasting 113 days.

For cohorts 3 to 7, planned subject participation will last up to 253 days, including a 28-day screening period prior to IP administration and on-study period (through the end of treatment visit) lasting 225 days.

For cohorts 8 and 9, planned subject participation will last up to 393 days, including a 28-day screening period prior to IP administration and on-study period (through the end of study visit) lasting 365 days.

For cohorts 1 to 7, the end of treatment visit will complete the subject's participation in this study unless a follow-up period is required. If there is a clinically significant clinical or laboratory abnormality that requires monitoring, subjects will be followed until resolution of the abnormality or until it is considered stable.

For cohorts 1 to 9, if at the end of treatment visit, the plasma Lp(a) level has not returned to  $\geq 80\%$  of baseline (mean of screening and day 1 predose), the follow-up period will be required.

The end of treatment visit for cohorts 8 and 9 will be the same as the end of study visit (day 365).

Subjects in cohorts 1 and 2 will return to the clinical study site approximately every 2 weeks until the Lp(a) level returns to  $\geq 80\%$  of baseline. Assessments during the follow-up period will include physical examination; vital signs; and collection of blood samples for chemistry, hematology, lipid, Lp(a), and biomarker development. When the protocol amendment 2 is implemented, the follow-up visits will continue approximately monthly, as needed, and will include only Lp(a) monitoring as described below for cohorts 3 to 7.

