#### **12.2.1.3      Serious Adverse Events after the Protocol-required Reporting Period**

There is no requirement to monitor study subjects for serious adverse events following the protocol-required reporting period or after end of study. However, these serious adverse events should be reported to Amgen (regardless of causality) if the investigator becomes aware of them. Per local requirements in some countries (eg, European Union [EU] member states), investigators are required to report serious adverse events that they become aware of after end of study. If serious adverse events are reported, the investigator is to report them to Amgen within 24 hours following the investigator's knowledge of the event.

Serious adverse events reported outside of the protocol-required reporting period will be captured within the safety database as clinical trial cases for the purposes of expedited reporting.

**If further safety related data is needed to fulfill any regulatory reporting requirements for a reportable event, then additional information may need to be collected from the subject's records after the subject ends the study.**

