### **13. STATISTICAL CONSIDERATIONS**

#### **13.1 Study Endpoints, Analysis Sets, and Covariates**

##### **13.1.1 Study Endpoints**

###### **13.1.1.1 Primary Endpoints**

- Subject incidence of treatment-emergent adverse events
- Safety laboratory analytes, vital signs, and electrocardiograms (ECGs)

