Randomization date is defined as the date subject was allocated a unique randomization number and assigned to either AMG 890 or placebo group.

Study Day 1

defined as the first day that investigational product is administered to the subject.

Study Day

Post study day 1: study day= (date of event-study day 1) +1

Pre-study day 1: study day= (date of event-study day 1)

Treatment-emergent Adverse Event during Treatment Period

A treatment-emergent adverse event during treatment period is any adverse event starting on or after the first dose of investigational product (as determined by the flag indicating if the adverse event started prior to the first dose or not on the Adverse Events eCRF) and up to and including the End of Treatment Date, **or EOS date for subjects who early discontinue the study during the treatment period.**

Treatment-emergent Serious Adverse Event during Follow-up Period

Subjects in cohorts 1-7 will be followed up for SAE reporting (every 2 weeks for cohorts 1-2 and monthly for cohorts 3-7) if the Lp(a) level has not returned to $\geq 80\%$ of baseline by the end of treatment visit. SAEs during the follow-up period are defined as any serious adverse event **categorized as Adverse Events (AEs) starting on or after first dose of investigational product (as determined by “Did event start before first dose of investigational product” equal to No or missing on the Events eCRF) and starting on or after the end of treatment date and up to and including the end of study date for an individual subject.**

If end of treatment and end of study is same for a subject, then the subject will only have TEAEs for treatment period derived.

For subjects in Cohort 8 and 9 the end of treatment and end of study is same i.e. day 365 so for those cohorts only TEAEs for treatment period will be derived.

6. Analysis Sets

For all analyses, subjects will be analyzed according to the dose and treatment they received, not the dose and treatment to which they were randomized.

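### The parenthesis in Protocol Section 12.2.1.2 can be read as ending SAE reporting at end of treatment in cohorts 1–7, while the schedules and SAP need SAEs from Lp(a) follow-up, so the follow-up SAE table may be incomplete

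*Protocol*

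**What the plan says.** Protocol Section 12.2.1.2 has investigators report SAEs from consent "through the end of study visit (last visit where data for primary endpoints are collected". The glossary entry on end of study for an individual subject reads "Defined as the last day that protocol-specified procedures are conducted for an individual subject". The synopsis, under End of Treatment, adds that a subject kept on because of Lp(a) has the end-of-study visit described under Follow-up.

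Non-serious events stop earlier. Section 12.2.1.1 covers events "that occur after the first dose of investigational product through the end of treatment visit are reported using the Event eCRF". End of treatment is day 113 in cohorts 1–2, day 225 in cohorts 3–7 and day 365 in cohorts 8–9. A cohort 1–7 subject whose Lp(a) is then below 80% of baseline goes into follow-up. Section 6.5.1 says of cohorts 1–2 that, once Amendment 2 is in force, these visits "will include only Lp(a) monitoring as described below for cohorts 3 to 7". The text for cohorts 3–7 describes roughly monthly visits for Lp(a) monitoring.

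Section 12.2.1.3 states: "There is no requirement to monitor study subjects for serious adverse events following the protocol-required reporting period or after end of study". It goes on to ask that any such SAE the investigator learns of be sent to the sponsor, whatever its cause, within 24 hours, and says that it is held in the safety database.

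SAP Section 5 states: "Subjects in cohorts 1-7 will be followed up for SAE reporting (every 2 weeks for cohorts 1-2 and monthly for cohorts 3-7". It defines follow-up SAEs through the Events eCRF, and SAP Section 9.6.1 tabulates them for cohorts 1–7. The synopsis, under Treatment, says: "All adverse events (including serious adverse events) and use of concomitant medication will be collected throughout the study".

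**The concern.** For a cohort 1–7 subject in follow-up, the protocol gives two possible ends to the SAE window within one sentence. If a site takes the parenthesis as the definition, and sees the visit described as Lp(a) monitoring only, it has reason not to ask about SAEs after day 113 or 225. The SAP nonetheless plans a table for exactly that period.

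The subjects in follow-up are those whose Lp(a) has stayed low longest, in a first-in-human study whose primary objective is safety. If SAEs were not solicited there, the table would present an absence of enquiry as an absence of events.

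**Working it through.** This is a reconciliation of text. The only arithmetic is a count of who could be affected.

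**Who could be affected (Table 1, planned numbers).**
- Cohorts 1–5: 5 × 6 = 30 AMG 890 and 5 × 2 = 10 placebo.
- Cohorts 6–7: 2 × 9 = 18 AMG 890 and 2 × 3 = 6 placebo.
- Cohorts 1–7 together: 30 + 18 = 48 AMG 890 and 10 + 6 = 16 placebo, 64 in all.
- Cohorts 8–9: 2 × 6 = 12 AMG 890 and 2 × 2 = 4 placebo.
- Share in cohorts 1–7: 64 / (64 + 16) = 80% of planned subjects.

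The 48 and 16 are ceilings. Only subjects below 80% of baseline Lp(a) at end of treatment enter follow-up, and the documents do not give their number.

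**Why cohorts 8–9 drop out.** One sentence in Section 6.5.1 extends the follow-up requirement to cohorts 1 to 9. The synopsis, the sentence after it in Section 6.5.1, Table 9 and SAP Section 5 all make day 365 both end of treatment and end of study for cohorts 8–9, so the two ends of the SAE window coincide.

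**Are SAEs inside the window during cohort 1–7 follow-up?**

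| Place | Reading |
|---|---|
| 12.2.1.2, operative words (end of study visit) with synopsis and glossary | Yes |
| 12.2.1.2, parenthesis | Most naturally no |
| Synopsis Follow-up and 6.5.1 | Lp(a) monitoring only; SAEs not mentioned |
| Table 5 | SAE row marked in the cohorts 3–5 monthly column, AE row blank there; the mark with footnote h appears to belong to cohorts 1–2 follow-up |
| Table 7 | SAE row marked in the follow-up column, AE row blank there |
| Synopsis, Treatment | Yes, and for all AEs, which conflicts with 12.2.1.1 |
| SAP 5 and 9.6.1 | Yes |

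Column alignment in Tables 5 and 7 is damaged in the text available. In Table 7 the marks for weight, eGFR and urinalysis also fall under follow-up, probably shifted from end of treatment. The contrast between the SAE and AE rows is clear enough to rely on; the exact list of other follow-up procedures is not.

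**Why the parenthesis points to end of treatment.** The primary endpoints are "Subject incidence of treatment-emergent adverse events" together with safety laboratory values, vital signs and ECGs. Non-serious AEs stop at end of treatment (12.2.1.1). The SAP's TEAE treatment period and the primary analysis data stop there too (SAP 5 and 7.2; Protocol 13.5.1). The current follow-up text lists no safety measurement. A reader looking for the last visit with primary-endpoint data would therefore settle on day 113 or 225.

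**Where an event would be recorded.** Within the reporting period, Section 12.2.1.2 sends an SAE to the Event eCRF and the paper report form. Outside it, Section 12.2.1.3 mentions only the safety database. The SAP derives follow-up SAEs from the eCRF. A site treating follow-up as out of period could therefore report an SAE correctly to the sponsor without its reaching the SAP table.

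**The case against.** The strongest reply is that the operative words already give the right answer. Section 12.2.1.1 runs non-serious AEs to end of treatment and Section 12.2.1.2 runs SAEs to end of study. That difference matches Tables 5 and 7, where SAEs but not AEs continue. The parenthesis can even be made to agree: the TEAE endpoint has no stated end-of-treatment limit, an SAE is an adverse event, and the SAP labels its follow-up category treatment-emergent. This stands as a possible and probably intended reading, and Section 9.5 itself speaks of additional safety follow-up in cohorts 1–7. It shows that the parenthesis is ambiguous, not that it is harmless.

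A reader might infer that SAE reporting simply stops at end of treatment, or that 24-hour reporting lapses in follow-up. The documents support neither. The first takes the parenthesis over the words it explains. The second overlooks Section 12.2.1.3, under which a known SAE still goes to the sponsor within 24 hours. What is left is the event nobody asked about, and the event that bypasses the eCRF.

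Two further points stand. The Lp(a)-only wording replaces a list of examinations and blood tests, so it may limit procedures rather than SAE enquiry; and before Amendment 2, follow-up in cohorts 1–2 included physical examination, vital signs, chemistry and hematology. Also, enrollment in cohorts 1–8 is closed and cohorts 1–5 had been dosed by February 2019, so a change to site instructions may come too late for most of these subjects.

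**Conclusion.** The conflict holds as one of wording: Section 12.2.1.2 supports the longer window by its main words and can be read as the shorter one by its parenthesis, while the schedules and SAP need the longer one. The consequence is possible incompleteness of the SAP's follow-up SAE table for cohorts 1–7, with at most 48 AMG 890 and 16 placebo subjects exposed to it. That SAEs were in fact missed cannot be shown from these documents.

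A reader might want to turn this into lost subject-years, but the documents give neither the proportion followed nor the duration. Assuming 20–80% of 48 followed for 3–12 months gives 48 × 0.2 × 0.25 = 2.4 to 48 × 0.8 × 1 = 38.4 subject-years on AMG 890. That 16-fold range comes from assumption alone. Section 6.5.1 also says that the planned durations were expected to let Lp(a) recover to 80% of baseline in each subject, which would make follow-up uncommon. The conclusion does not rest on this figure.

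With cohorts 1–7 closed to enrollment, the main value now lies in how the follow-up table is interpreted.

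**What to change.** Reconcile the passages:

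- In Section 12.2.1.2, delete the parenthesis, or replace it with *including any Lp(a) follow-up visits*.
- In the synopsis and Section 6.5.1, state that follow-up visits comprise Lp(a) monitoring and SAE collection, as Tables 5 and 7 already show.
- Align the synopsis sentence on collecting all AEs for the whole study with Section 12.2.1.1.
- For follow-up already completed, add a footnote to the SAP follow-up SAE table saying whether SAEs were actively solicited at those visits.

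If the SAP is opened for this, one neighbouring detail can be settled with it: Section 5 places the end-of-treatment date in both the treatment period and the follow-up period, so an SAE starting that day could be counted twice.

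The cost is protocol wording, a memo to sites and a table footnote. No visit or procedure is added, because the subject already attends and the schedule already carries the SAE item. The footnote is useful even if all follow-up is finished.
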